3.9 Safety Analysis

All safety analyses will be based on the SS. Descriptive statistics will be used to summarize all safety endpoints by treatment group. Data summaries will be displayed for incidence of TEAEs, clinical laboratory variables, vital signs, body weight and body mass index, physical examinations, clinical assessment of suicidality (ABC-I) and seizure diary data.

Unless otherwise specified below, safety data for subjects 2 to 3 years old (inclusive) will only be presented in listings and will be displayed in by-subject graphs, as appropriate.

3.9.1 Adverse Events

All adverse events will be coded using the MedDRA Version 22.0 and will be classified by MedDRA SOC and PT. Analyses of adverse events will be performed using the SS.

AEs that started on or after the first dose of study medication or worsened after the first dose of study medication through 14 days after the last dose of study medication and 30 days after the last dose of study drug/last study visit for SAEs are considered treatment-emergent AEs (TEAEs).

For all summaries, SOCs and PTs within SOC will be presented by decreasing frequency of incidence, sorted first for the OV101 group and then for the placebo group.

Handling of Missing or Partial Start Dates for Adverse Events

Rules for handling incomplete or missing adverse event start dates are addressed below (stop dates will not be imputed).

In the unusual case that the month portion of an adverse event start date is missing but the day portion is not missing, the day portion will be assumed to be missing.

Likewise, in the case where the year portion of an adverse event start date is missing but the month and/or day portion is not missing, the month and/or day portion will be assumed to be missing. All missing portion(s) of the date will be handled using the same rules:

- In the event that the day portion (and only the day portion) of the date is missing:
 - If the adverse event started in the same month and year as the first dose date, the adverse event start date will be assumed to be the first dose date.
 - Otherwise, the adverse event start date will be assumed to be the last day of the given month and year, e.g., XX–DEC-2005 would be 31-DEC-2005 where XX represents an unknown day.
- In the event that the day and month portions (and only the day and month portions) of the date are missing:
 - If the adverse event started in the same year as the first dose date, the adverse event start date will be assumed to be the first dose date.
 - Otherwise, the adverse event start date will be assumed to be last month and day of the given year, e.g., XX–XXX-2005 would be 31-DEC-2005 where XX represents an unknown day and XXX represents an unknown month.

- In the event that the day, month, and year portions of the adverse event start date are missing, it will be assumed to be the first dose date.
- If the adverse event start date has been imputed using the rules above, then the adverse event start date must be compared with the adverse event stop date to ensure the logical ordering of dates. If the imputed adverse event start date is after the non-missing adverse event stop date, then the imputed start date will be reset as the stop date.

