3.6 Prior and Concomitant Medications

Prior medications are defined as medications that started before first study drug administration and either stopped before or continued after first study drug administration. Concomitant medications are defined as medications that are being taken while on study drug. Medications that are ongoing on the date of the first administration of study drug will be classified as both prior and concomitant. Any medication that cannot be confirmed as stopping before the start of study drug will be classified as both a prior and a concomitant medication.

Partial medication dates will be imputed with maximum conservatism when determining if a medication is concomitant. If the onset date is missing or partial, the date will be compared as far as possible with the date of first dose of study medication. If no month is present and it is in the same year as the date of first treatment, or the year and month are the same as the first treatment date, the onset date will be imputed as the date of first treatment. Otherwise it will be imputed as 01 January in the available year, or the first day of the month and year available. End dates will be imputed as 31 December in the available year, or the last day of the available month and year collected. The imputed start date must be less than or equal to the imputed stop date.

All medications will be coded with the WHO Drug Dictionary (WHO-DD B3 format, March 2019). Prior and concomitant medications will be summarized separately and the number and percentage of subjects in each treatment group who took at least one

prior (concomitant) medication as well as the number and percentage of subjects who took each type of medication will be summarized separately for subjects 4-12 years old (inclusive) and subjects 2-3 years old (inclusive) by Anatomic Therapeutic Class (ATC) Level 2, ATC Level 4, and Preferred Term (PT) for the SS. If a subject has more than one occurrence of the same PT, then the PT will be counted only once for that subject. Similarly, if a subject has more than one PT within ATC Level 4 or ATC Level 4 within ATC Level 2, then the subject will be counted only once in that ATC Level 4 or ATC Level 2.

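### Two branches of the SAP's AE start-date imputation use the latest possible date with no cap, so a few on-treatment AEs with partial dates can fall outside the TEAE window (minor)

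*SAP*

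**What the plan says.** SAP 3.9.1 puts an upper bound on the TEAE definition: "through 14 days after the last dose of study medication and 30 days after the last dose of study drug/last study visit for SAEs". The protocol's definition (6.4.1.1) covers any AE that starts or worsens after first dose and has no upper bound.

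The date rules in SAP 3.9.1 are:

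- **Day missing.** "If the adverse event started in the same month and year as the first dose date", the first dose date is used. "Otherwise, the adverse event start date will be assumed to be the last day of the given month and year".
- **Day and month missing.** "If the adverse event started in the same year as the first dose date", the first dose date is used. "Otherwise, the adverse event start date will be assumed to be last month and day of the given year".
- **Whole date missing.** "it will be assumed to be the first dose date".
- **Stop-date check.** An imputed start later than a known stop date is reset to that stop date. Stop dates themselves are not imputed.

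For medication onset, SAP 3.6 goes to the other end of the interval: "Otherwise it will be imputed as 01 January in the available year, or the first day of the month and year available". SAP 3.1.6.2 describes the medication rule as maximally conservative.

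**The concern.** The imputed start date decides whether an AE counts as treatment-emergent. In the two residual branches the date is pushed as late as the known parts allow, and nothing keeps it inside the window. An AE that began on study drug can then drop out of the TEAE summaries: incidence, severity, relatedness and events of special interest (SAP 3.9.1.1 to 3.9.1.3 and 3.9.1.6).

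The rules are also out of order with each other. An AE with no start date at all is kept as a TEAE, while the same AE with its month known can be dropped. Safety rules normally resolve doubtful timing towards inclusion, as the SAP does for medications.

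The stop-date check does not close the gap. AE follow-up ends at resolution or 14 days after last dose, whichever is first (protocol 6.4.1.3), so an unresolved AE may have no stop date. Children entering ELARA finish NEPTUNE at Week 12. The exposed events lie mainly near the end of treatment.

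**Working it through.** **Inputs.** TEAE window and imputation rules: SAP 3.9.1. Treatment length: 12 weeks = 84 days (SAP 2.2). Assumptions not in the documents: first-dose dates uniform over a 365-day year, AE onsets uniform over treatment days, full treatment length.

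**The plan's own example.** An unknown day in December 2005, outside the first-dose month, is imputed to 31-DEC-2005. Coding the rule returns the same date.

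**One child.** First dose 15-JAN-2020, so last dose = 15-JAN + 83 days = 07-APR-2020, and the window ends on 21-APR-2020. An AE begins on 02-APR, on treatment, and is recorded as XX-APR-2020.

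| Stop date | Imputed start | TEAE? |
|---|---|---|
| None (ongoing) | 30-APR | No |
| 06-APR | 06-APR (reset) | Yes |
| 25-APR | 25-APR (reset) | No |

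**When it can happen, day missing.** The month-end must fall more than 14 days after last dose. That requires a last dose on or before day 16 of a 31-day month (31 − 16 = 15), day 15 of a 30-day month or day 13 of a 28-day month. This covers 50.7% of last-dose dates.

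**Enumeration, day missing, no stop date.** 365 first-dose dates × 84 onset days = 30,660 combinations. An AE is lost if its imputed start is later than last dose + 14 days.

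- All on-treatment onsets: 1,523 / 30,660 = 5.0%.
- Last 14 treatment days: 1,498 / (365 × 14 = 5,110) = 29.3%.
- With 85 treatment days the overall figure is 4.9%.

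**Effect of a known stop date on the day-missing loss.** 0% for AEs lasting 14 days or less, 3.0% at 21 days, 4.8% at 28 days.

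**SAEs, day missing.** The gap from last dose to month-end is at most 30 days and the window is 30 days, so no on-treatment SAE is lost.

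**Year only, no stop date.** If treatment crosses a year end, every onset in the second year is moved to 31 December of that year. Example: first dose 20-NOV-2020, last dose 11-FEB-2021. An AE in 2021 is imputed to 31-DEC-2021, beyond both 25-FEB (14 days) and 13-MAR (30 days). Over all first-dose dates the loss is 3,486 / 30,660 = 11.4%. Among treatment courses that cross a year end (83 first-dose dates × 84 = 6,972) it is 3,486 / 6,972 = 50%. SAEs are lost at the same rate.

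**After the fix.** The first day of the known month, or 1 January of the known year, cannot be later than the true onset. No onset inside the window is then moved out of it: 0 lost. In these branches a date in a later month or year than first dose also stays after first dose.

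**The case against.** The best case against the point is that its reach is narrow.

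- **Most branches are already inclusive.** Partial dates in the first-dose month or year, and wholly missing dates, go to the first dose date. A reader might infer that all partial AE dates are set as late as possible; the text does not support that.
- **The stop-date check works where it applies.** Any AE with a known stop date inside the window is kept.
- **SAEs are largely protected.** A reader might infer that serious events are lost generally. With only the day missing, no on-treatment SAE is; only year-only SAEs are exposed.
- **Events leave tables, not the report.** SAP 3.9.1.4 summarises deaths, other SAEs and AEs leading to discontinuation without a stated TEAE restriction, and SAP 3.1.2 puts all data in listings. The rule is the same in both arms and safety is descriptive, so the documents show no between-arm bias.
- **Year-only dates should be rare.** Time of onset is a required AE item (protocol 6.4.1.4), and AEs are asked about at every visit and call in a study of about 18 weeks.
- **The window sentence is loosely built.** The 14-day limit could be read as bounding only worsening. Bounding both starts and worsenings is the natural reading, but under the protocol's definition nothing would be dropped.

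It is also tempting to call the imputed date impossible, because AE collection stops 14 days after last dose. That fails for SAEs, which are reportable to 30 days and, if related, later. It is also not general for other AEs, since ELARA entrants are excepted from the 14-day collection.

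All of this limits the size of the problem. None of it gives a reason for choosing the latest date or for leaving it uncapped.

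**Conclusion.** The point holds in narrow form, at minor severity. Followed exactly, the SAP can remove from the TEAE tables (a) a non-serious on-treatment AE with only its day missing and no stop date by last dose + 14 days, and (b) a year-only AE or SAE with no stop date inside its window, when treatment crosses a year end.

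Among such AEs without a protective stop date, about 5% of day-missing on-treatment onsets are lost overall, 29% of those in the last 14 treatment days, and about 11% of year-only onsets. These shares rest on the uniform-date and full-treatment assumptions. They apply only to partially dated AEs, and the documents give no rate for those.

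As an illustration for day-missing dates, with all inputs but the 5% assumed: 300 AEs, 2% to 10% with the day missing, 20% to 50% of these unprotected, and 5% lost gives 300 × 0.02 × 0.20 × 0.05 = 0.06 to 300 × 0.10 × 0.50 × 0.05 = 0.75 events in the trial. With about 45 children per arm, one child lost from a row moves an incidence by 1/45 = 2.2 percentage points.

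**What to change.** In SAP 3.9.1:

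1. In the two residual branches, impute to the first day of the known month, or to 1 January of the known year.
2. Keep the first-dose branches and the stop-date check unchanged.
3. State that a partially dated AE counts as treatment-emergent unless its known date parts prove onset before first dose or after the window (14 days; 30 days for SAEs).
4. Reconcile the bounded TEAE definition with the unbounded one in protocol 6.4.1.1, and make clear that the bound applies to starts as well as worsenings if that is intended.

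While editing, correct SAP 3.1.6.2, which points to section 3.8.1 for these rules; they are in 3.9.1.

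The cost is a few lines of SAP text and one programming rule. AE counts may rise slightly, because an event that truly began after the window but is known only to the month or year can now be counted. Efficacy analyses are untouched.

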3.9.1.1 Overall Summary of AEs

An overall summary of TEAEs will be presented by treatment group. The number and percentage of subjects who experienced at least one TEAE, at least one mild TEAE, at least one moderate TEAE, at least one severe TEAE, at least one TEAE leading to dose change/interruption, at least one TEAE leading to study drug discontinuation, at least one TEAE leading to study withdrawal, at least one treatment-related TEAE, at least one serious TEAE, at least one treatment-related serious TEAE, and a TEAE leading to death will be displayed. Treatment-related TEAEs are events with a study drug causality of ‘possible’, ‘probable’ or ‘definite.’

Incidence of AEs will be summarized separately for subjects 2 to 3 years old (inclusive).

3.9.1.2 AE Incidences

The incidence of TEAEs will be presented by actual age group (4-8 versus 9-12 years old) and treatment group. The number and percentage of subjects who experienced at least one TEAE as well as the number and percentage of subjects who experienced each specific SOC and PT will be presented. For this analysis, if a subject has more than one occurrence of the same PT, then the PT will be counted only once for that subject. Similarly, if a subject has more than one occurrence of the same PT within a SOC, the subject will be counted only once in that SOC.

A summary table by PT only will be presented using the same methods as described above for the by SOC and PT summary table. Additionally, the incidence of TEAE within each specific SOC, HLGT, and PT and specific SOC, HLT, and PT will be presented. The incidence of TEAEs by SOC/PT and maximum severity will also be presented.

For subjects 2 to 3 years old, a summary table by SOC and PT, by PT, and the incidence of TEAEs by PT and maximum severity will be presented.

All TEAEs will be included in a subject listing.

3.9.1.3 Related AEs

The incidence of drug-related TEAEs will be presented by actual age group (4-8 versus 9-12 years old) and treatment group. Related TEAEs will be defined as those with a 'possible', 'probable' or 'definite' relationship to treatment. TEAEs with missing relationship will be counted as related. For this analysis, if a subject has more than one occurrence of the same PT, then the PT will be counted only once for that subject. Similarly, if a subject has more than one occurrence of the same PT within a SOC, the subject will be counted only once in that SOC.

A summary table of drug-related TEAEs will also be presented for subjects 2 to 3 years old. These tables will be repeated for drug-related serious AEs.

3.9.1.4 Deaths, Other Serious AEs and AEs That Led to Treatment Discontinuation

Summaries of deaths, other serious AEs, and AEs that led to treatment discontinuation will be presented by actual age group (4-8 versus 9-12 years old) and treatment group. A summary of serious AEs, and AEs that led to treatment discontinuation will also be presented for subjects 2 to 3 years old. Adverse events that led to study withdrawal will be shown in a listing.

3.9.1.5 AEs That Led to Study Drug Interruption

All adverse events that resulted in study drug interruption will be included in a by-subject listing.

3.9.1.6 AEs of Special Interest

Adverse events of special interest include the following categories:

- Sleep Disorders and Disturbances (HLGT)
- Seizures (Including Subtypes) (HLGT)

All AEs of special interest will be identified by using the above MedDRA PTs during a blinded review of the data.

The incidence of TEAEs of special interest by actual age group (4-8 versus 9-12 years old) and treatment group will be presented separately for each term. The number and percentage of subjects who experienced at least one TEAE of special interest as well as the number and percentage of subjects who experienced each specific SOC and PT will be presented. For this analysis, if a subject has more than one occurrence of the same PT, then the PT will be counted only once for that subject (e.g., subject incidence). Similarly, if a subject has more than one occurrence of the same PT within a SOC, the subject will be counted only once in that SOC.

3.9.2 Clinical Laboratory Evaluation

A list of clinical laboratory tests is given below:

Hematology	
 - Hematocrit - Hemoglobin - Red blood cell count - Mean corpuscular volume - Mean corpuscular hemoglobin - Mean corpuscular hemoglobin concentration - Reticulocytes - White blood cell count 	
 - Neutrophils (% and count) - Lymphocytes (% and count) - Monocytes (% and count) - Eosinophils (% and count) - Basophils (% and count) - Platelet count - Prothrombin time - Partial thromboplastin time - International normalization ratio
Clinical Chemistry	
 - Albumin - Alkaline phosphatase - Blood urea nitrogen - Gamma-glutamyl transferase - Calcium - Creatinine - Glucose - Cholesterol, high-density lipoprotein [calculated] - Cholesterol, low-density lipoprotein [calculated] - Cholesterol, homogenous low-density lipoprotein - Triglycerides 	
 - Magnesium - Phosphate - Potassium - Alanine aminotransferase - Aspartate aminotransferase - Lactate dehydrogenase - Sodium - Chloride - Total bilirubin - Direct bilirubin - Total protein - Uric acid - Creatine phosphokinase
Pregnancy Testing¹	
 - Serum β-hCG or urine pregnancy testing for female subjects who have experienced menarche 	

¹ Pregnancy testing parameter will be listed only.

Continuous laboratory data will be examined for trends using descriptive statistics of observed values and changes from baseline to each planned post-baseline visit. These data will also be categorized as low, normal or high based on the reference ranges of the central/local laboratory. Frequencies and percentages will be presented for the shifts in these categories from baseline to each post-baseline visit (i.e., low to normal, low to high, high to low, etc.) for all applicable laboratory parameters listed above. The analyses will be performed using the SS and presented by treatment group.

A separate listing for all clinically significant laboratory abnormalities will be provided.

3.9.3 Vital Signs and Other Physical Findings

Vital signs (temperature, heart rate, respiratory rate, and systolic and diastolic blood pressure), weight, and body mass index will be summarized descriptively at Baseline and all post-Baseline study visits by treatment group. Values will be categorized

based on reference ranges by age group as normal, low abnormal, and high abnormal (see section 4.1.8). Shift from Baseline to all post-Baseline study visits for these categories will be summarized descriptively by treatment group.

All vital sign results will be included in a subject listing.

3.9.4 Physical Examination

Physical examinations (general appearance; skin; head, ear, eye, nose, and throat; neck; lymph node; chest; heart; abdominal cavity; limb; central nervous system; and musculoskeletal) will be performed.

Whether or not a physical examination was conducted with date performed will be included in a subject listing.

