6.4.1.3 Eliciting and Documenting Adverse Events

Adverse events will be assessed beginning on the date of signed informed consent and up to 14 days after the last dose of study drug (unless a subject decides to participate in the ELARA open-label extension study) and must be followed until resolution or for 14 days after the subject's last study drug dose, whichever comes first.

Serious AEs that occur more than 30 days after the last dose of study drug need not be reported unless the investigator considers them related to study drug.

After informed consent is obtained, at every clinic visit and phone visit, subjects and their LAR/caregiver will be asked a standard nonleading question to elicit any medically-related changes in their well-being. They will also be asked if they have been hospitalized, had any accidents, used any new medications, or changed concomitant medication regimens (both prescription and over-the-counter medications).

In addition to subject observations, AEs identified from any study data (e.g., laboratory values, physical examination findings) or identified from the review of other documents (e.g., subject diaries) that are relevant to subject safety or considered to be clinically significant, in the medical and scientific judgment of the investigator, will be documented on the AE page in the eCRF.

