7.2.2 Safety Endpoints

- Incidence of AEs
- Change in clinical laboratory parameters from baseline to each post baseline assessment
- Shift in clinical laboratory parameters from baseline to each post baseline assessment
- Change in vital sign measurements from baseline to each post baseline assessment
- Shift in physical examination parameters from baseline to each post baseline assessment
- Change in suicidality assessment (ABC-I) from baseline to each postbaseline as assessed by ABC-I. The ABC-I will serve as a surrogate measure for suicidality
- Percent change in seizure frequency (expressed as a 28-day frequency) from baseline to each post baseline timepoint

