7.9.3 Vital Signs and Physical Examinations

Vital signs (systolic and diastolic blood pressure, temperature, heart rate, and respiratory rate), weight, and body mass index will be summarized descriptively at baseline and all post baseline study visits by treatment group. Change from baseline to all post baseline study visits will be summarized descriptively by treatment group.

Physical examinations (general appearance; skin; head, ears, eyes, nose, and throat; neck; lymph nodes; chest (including lungs); heart; abdomen; extremities; nervous system; and musculoskeletal system) at baseline will be summarized. Shifts from baseline to post baseline study visits in each body system/site will be summarized by treatment group.

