3.3.6 Safety Endpoints

- Incidence of adverse events
- Change in clinical laboratory parameters from Baseline to each post-baseline assessment
- Shift in clinical laboratory parameters from Baseline to each post-baseline assessment
- Change and shift in vital sign measurements from Baseline to each post-baseline assessment

- Change in suicidality assessment (ABC-I) from Baseline to each post-baseline assessment. The ABC-I will serve as a surrogate measure for suicidality
- Percent change in seizure frequency (collected in seizure diary) per 28 days from Baseline to each post-baseline time point

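### The SAP omits the protocol's physical-examination shift endpoint and specifies only a performed/date listing, while its own general safety section still promises a summary

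*SAP*

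**What the plan says.** Protocol 7.2.2 gives seven safety endpoints. One is "Shift in physical examination parameters from baseline to each post baseline assessment". Protocol 7.9.3 sets out the analysis: baseline examinations are summarised over 11 body systems or sites, and then "Shifts from baseline to post baseline study visits in each body system/site will be summarized by treatment group". The statistical methods part of the synopsis plans the same.

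SAP 3.3.6 gives six safety endpoints, none of them about the physical examination. SAP 3.9.4 names the body systems, says that they will be examined, and then defines a single output: "Whether or not a physical examination was conducted with date performed will be included in a subject listing".

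SAP 3.9, which introduces all the safety analyses, says: "Data summaries will be displayed for incidence of TEAEs, clinical laboratory variables, vital signs, body weight and body mass index, physical examinations", and continues with the ABC-I and the seizure diary.

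Protocol 7.1 requires an amendment for a substantial change to the analysis methods. Any other change is to be described in the SAP together with its justification.

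**The concern.** A safety endpoint that the protocol names, with a by-arm analysis, has no corresponding table in the SAP. A programmer cannot tell which SAP section governs: 3.9 asks for a summary, while 3.9.4 defines nothing to summarise beyond whether and when the examination took place. If 3.9.4 is followed, the study report will lack a stated safety endpoint, and a reader of the report will find no explanation in the SAP.

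At stake is how completely safety is described in a paediatric trial. The shift table would show, by arm, changes in examination status that nobody recorded as an adverse event. No hypothesis test or efficacy estimate depends on it.

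**Working it through.** The plan gives no figure to reproduce and no formula applies, so the check is a comparison of text.

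1. **Endpoint lists.** Protocol 7.2.2 has seven items: AE incidence, laboratory change, laboratory shift, vital-sign change, physical-examination shift, ABC-I change and seizure-frequency change. SAP 3.3.6 has six: AE incidence, laboratory change, laboratory shift, a vital-sign item, ABC-I change and seizure-frequency change. The difference is 7 − 6 = 1, the physical-examination shift.

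2. **Was the list edited or merely shortened?** The SAP's vital-sign item reads "Change and shift in vital sign measurements from Baseline to each post-baseline assessment". The protocol's item covers change only. The SAP therefore added a shift for vital signs in the same list from which the examination shift is absent. The documents do not say whether that absence was intended.

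3. **Dedicated sections.** Protocol 7.9.3 specifies a baseline summary and a by-arm shift summary. SAP 3.9.4 names the same 11 systems or sites in slightly different words, with neither summary. By contrast, SAP 3.9.2 and 3.9.3 do specify shift summaries for laboratory tests and vital signs.

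4. **Does a general SAP statement fill the gap?** SAP 3.9 says "Descriptive statistics will be used to summarize all safety endpoints by treatment group", but that reaches only what the SAP lists as a safety endpoint, and the examination shift is no longer there. The next sentence of 3.9 does name physical examinations, but gives no content, categories or time points for the summary. SAP 3.1.2 promises listings of all clinical data and summaries of all endpoints; a listing is not a by-arm shift table.

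5. **Justification.** Neither SAP 3.3.6 nor 3.9.4 explains the change, and no other section of the supplied SAP does so. SAP Section 1 says that its methods are based on Section 7 of the protocol. Neither SAP section shows a redaction mark that would account for the omission.

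6. **What still reaches a by-arm table.** Protocol 6.4.1.3 sends to the AE page "AEs identified from any study data (e.g., laboratory values, physical examination findings" among its examples, where the investigator considers them relevant to safety or clinically significant. Protocol 6.4.1.4 adds conditions present at screening that worsen. Protocol 6.4.1.8 says to report when in doubt. SAP 3.9.1.2 tabulates the treatment-emergent events by treatment group. Weight, taken at the examination (protocol 6.4.2.4), is summarised by arm with BMI in SAP 3.9.3.

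7. **What does not.** Shifts to abnormal that meet none of those AE criteria, and shifts from abnormal to normal, which would not be adverse events. The documents give no basis for estimating how many there would be.

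8. **Population.** About 95 children are enrolled. About 5 of them, aged 2 to 3, all receive OV101, and under protocol 7.9 and SAP 3.9 their safety data are presented as listings and by-subject graphs unless otherwise specified. The by-arm table therefore concerns 95 − 5 = about 90 randomised children.

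**The case against.** The best defence is that little safety information is lost. The AE capture rule is broad: relevance to safety is enough without clinical significance, worsening of an existing condition counts, and doubtful observations are reported. Those events are tabulated by arm, by system organ class and preferred term, and by maximum severity. SAP 3.9 also still commits to summarising examinations. This stands, and it limits the consequence to shifts that are not adverse events. It does not remove the mismatch, because the protocol lists AE incidence and the examination shift as separate endpoints, and a promise without a defined table is not a specification.

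A reader might infer that examination findings will never be summarised by treatment group. The documents do not support that: SAP 3.9 says the opposite, recorded findings appear in the TEAE tables, and weight and BMI are summarised by arm. Nor do they support a special concern about nervous-system or musculoskeletal findings, which are treated like any other system.

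A second defence is that the eCRF may record only performed/date, so that no shift table is possible. SAP 3.9.4 is consistent with this, and protocol 6.4.2.4 describes only a general assessment of each system. The documents do not settle it. If it is so, the SAP should say so and the endpoint cannot remain in the protocol as written.

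Third, the SAP is written to protocol version 4.0, which is not available here; the protocol supplied is Version 6.0. Whether version 4.0 contained the endpoint cannot be checked. The amendment that led to Version 6.0 is described as administrative only. In either case the current protocol and the SAP conflict.

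**Conclusion.** The point holds as a gap between the protocol and the SAP, together with an inconsistency inside the SAP. One of seven protocol safety endpoints, covering 11 body systems or sites in about 90 randomised children, has no specified table, and its removal is not justified as protocol 7.1 requires. The practical loss is the by-arm tabulation of body-system shifts that do not become adverse events. It is a minor matter of completeness and traceability with no bearing on the efficacy inference.

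The conclusion assumes that the supplied text of SAP 3.3.6 and 3.9.4 is complete, and that examination findings are recorded as AEs in line with protocol 6.4.1.3, 6.4.1.4 and 6.4.1.8. The number of post-baseline examinations is left open, because the schedule table is not in the supplied text.

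**What to change.** First establish whether the eCRF records a result for each body system.

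- **If it does:** restore the shift endpoint in SAP 3.3.6. Add to SAP 3.9.4 a table of shifts (normal/abnormal) from baseline to each post-baseline examination, by body system and treatment group, for the randomised children, with a listing of new abnormal findings. The promise in SAP 3.9 then has a defined output. Cost: one table and one listing.
- **If it does not:** state in the SAP that the endpoint is removed and why, say that examination findings are reported through adverse events, delete physical examinations from the summaries promised in SAP 3.9, and align protocol 7.2.2 and 7.9.3. If the sponsor regards the change as not substantial, protocol 7.1 is met by the justified statement in the SAP, and the protocol text can be aligned at its next revision. Cost: one justified SAP statement and the alignment of the wording.

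Either route should be completed before database lock and unblinding.
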